APRI	AST to Platelet Ratio Index		
AST	Aspartate Aminotransferase		
BID	Twice Daily		
CK-18	Cytokeratin-18		
CSR	Clinical Study Report		
DBP	Diastolic Blood Pressure		
ECG	Electrocardiogram		
eCRF	Electronic Case Report Form		
ELF	Enhanced Liver Fibrosis		
FDA	Food and Drug Administration		
FIB-4	Fibrosis-4		
GGT	Gamma Glutamyl Transferase		
hsCRP	High Sensitivity C-Reactive Protein		
ICH	International Conference on Harmonization		
lgM	Immunoglobulin M		
IMP	Investigational Medicinal Product		
IPF	Idiopathic Pulmonary Fibrosis		
ITT	Intent-To-Treat		
IWRS	Interactive Web-Based Randomization System		
LOCF	Last Observation Carried Forward		
MSAP	Modeling and Simulation Analysis Plan		
NADPH	Nicotinamide Adenine Dinucleotide Phosphate		
OCA	Obeticholic Acid		
OD	Once Daily		
РВС	Primary Biliary Cholangitis		

PD	Pharmacodynamic		
РК	Pharmacokinetic		
PP	Per Protocol		
QTcF	Corrected QT Interval (Fredericia's Formula)		
SAP	Statistical Analysis Plan		
SBP	Systolic Blood Pressure		
SMB	Safety Monitoring Board		
TEAE	Treatment-Emergent Adverse Event		
TSH	Thyroid-Stimulating Hormone		
UDCA	Ursodeoxycholic Acid		
ULN	Upper Limit Of Normal		
VAS	Visual Analog Scale		
WHO	World Health Organization		

3 Introduction

The purpose of this document is to describe the statistical methods, data derivations and data summaries to be employed in the analysis of study GSN000300 set up by Genkyotex in order to assess the efficacy and safety of oral GKT137831, a selective inhibitor of NOX 1 and 4 isoforms of the Nicotinamide Adenine Dinucleotide Phosphate (NADPH) oxidase family of enzymes, in patients with primary biliary cholangitis (PBC) receiving ursodeoxycholic acid (UDCA) and with persistently elevated alkaline phosphatase (ALP).

The preparation of this statistical analysis plan (SAP) has been based on International Conference on Harmonisation (ICH) E3 and E9 Guidelines and in reference to Protocol GSN000300 Version 4.0 (Amendment 3, 24 July 2018) and CRF Version 6.4 (12 February 2019).

4 Study Objectives

PRIMARY OBJECTIVE

The primary objective of the study is defined as follows:

• To evaluate the efficacy of oral GKT137831 in comparison with placebo, in subjects with PBC receiving UDCA and with persistently elevated serum ALP.

SECONDARY OBJECTIVES

The secondary objectives of the study are defined as follows:

- To evaluate the safety of oral GKT137831 in comparison with placebo, in subjects with PBC receiving UDCA and with persistently elevated serum ALP.
- To estimate the pharmacokinetics (PK) population of GKT137831 and explore any potential PK-PD (pharmacodynamics) relationships in this subject population.
- To explore any relationship between genetic parameters and therapeutic responses in a subset of subjects.

5 Study Design

5.1 STUDY DESIGN AND POPULATION

The study population consists of approximately 100 subjects with PBC receiving a stable dose of UDCA and with persistently elevated ALP.

The study is a double-blind, randomized, placebo-controlled, multicenter, parallel group phase 2 trial assessing a 24-week period of treatment with oral GKT137831 administered in addition to standard of care medication (UDCA) in subjects with PBC. Subjects will be followed up for 28 days after the end of the treatment period.

An overview of the study design is presented in Figure 1 below.

[figure not shown]

Figure 1: Study Design Flowchart

5.2 STUDY TREATMENTS AND ASSESSMENTS

Subjects will be assessed for their eligibility during the screening period (Visit 1), which will last up to 4 weeks, until the baseline/Day 1 visit (Visit 2).

Eligible subjects will be allocated to oral GKT137831 (400 mg Once Daily (OD) or 400 mg Twice Daily (BID) or placebo, according to a 1:1:1 randomization ratio stratified by disease severity level at study entry defined as baseline serum Gamma Glutamyl Transferase (GGT) < 2.5 x Upper Limit of Normal (ULN) or \geq 2.5 x ULN.

Subjects will self-administer orally 400 mg OD or 400 mg BID of oral GKT137831 or matching placebo for a total of 24 weeks.

Baseline assessments will be performed at baseline/Day 1 (Visit 2). The 24-week treatment period will include assessments after 2 weeks of treatment (Visit 3), after 6 weeks of treatment (Visit 4), after 12 weeks of treatment (Visit 5), after 18 weeks of treatment (Visit 6) and after 24 weeks of treatment (End of Treatment/Visit 7). Subjects will be followed up to 28 days after the end of treatment (Week 28/Visit 8), totaling 6 post-baseline visits. Subjects who discontinue treatment before Week 24 visit will attend an Early Termination visit (premature end of treatment).

Pharmacokinetic samples will be taken at baseline, Week 2, Week 12 and Week 18 visits (see Protocol Version 3.0 - Section 8.8.2 for further details regarding the sampling time points).

Subjects will be taking a stable dose of UDCA at enrollment and will continue their UDCA treatment at a stable dose (no changes at all) during the treatment period.

A Safety Monitoring Board will oversee the conduct of the study to ensure the safety of

Template Author: [name] Version 3.0 16AUG2017

participating subjects (see Protocol Version 3.0 - Section 9.7 for more details). An interim analysis will be conducted when at least 80-90% of the planned number of subjects to be randomized in the study have completed their Week 6 visit (see Section 9). This IA analysis will assess demographics and efficacy data collected up to Week 6.

5.3 RANDOMIZATION AND BLINDING

Approximately 100 subjects will be randomly allocated to placebo or one of the 2 active treatment arms, according to a 1:1:1 randomization ratio stratified at study entry by disease severity level defined as baseline serum GGT < $2.5 \times ULN$ or $\geq 2.5 \times ULN$).

Accordingly, approximately 33-34 subjects will be allocated to each of the 3 treatment arms.

A master reproducible randomization list will be produced by or under the responsibility of Cmed accounting for block size and stratification. The Interactive Web-Based Randomization System (IWRS) will assign a unique randomization number in ascending, sequential order (with associated treatment arm) to the subject, based on the pre-determined randomization schedule. The system will assign the pre-determined blocks of randomization numbers for each stratification level to ensure similarly balanced treatment groups. Assignment will be in sequential order within blocks and stratification level. The investigator will enter the randomization number in the electronic case report form (eCRF).

The Sponsor, subjects, investigator staff, persons performing the assessments, data reviewers and statisticians will remain blinded to the identity of the study treatments.

The identity of the study treatments will be concealed by the use of Investigational Medicinal Products (IMPs) which are all identical in packaging, labeling, schedule of administration, appearance and odor.

Randomization data will be kept strictly confidential and be accessible only to authorized personnel (e.g., unblinded pharmacist or authorized designee), until unblinding of the trial as described in this SAP.

Unblinding will only occur for the following reasons:

- Subject emergencies (see Protocol Section 5.6.3 for more details)
- Scheduled and unscheduled safety reviews by the Safety Monitoring Board (SMB) (see Protocol Section 9.7 for more details)
- At the time of the interim analysis (see Section 9)
- At the end of the study.

5.4 SAMPLE SIZE JUSTIFICATION

A sample size of 34 randomly allocated and treated subjects within each treatment group with an overall sample size of 102 subjects will have 80% power to detect a 28% difference in the means of the percent change from baseline in serum GGT. A Wilcoxon Mann-Whitney test has been used for the sample size estimate because this represents the worst-case scenario with regards to the statistical power. A standard deviation of 30 for the active GKT137831 group and a standard deviation of 40 for the placebo group have been assumed based on a recent phase 3 clinical trial of OCA [1].

An overall two-sided Type I error of 5% has been considered for the sample size calculation. The Hochberg method will be used to adjust the alpha level for multiple comparisons. Therefore, the first dose level comparison at the final analysis will be tested against an alpha level of 0.04695 and the second dose level will be tested against an alpha level of 0.023475. The alpha level of 0.023475 has been used for the sample size calculation.

The sample size calculation assumes all subjects (including withdrawals) will be included in the analysis. As a result, there has been no adjustment for dropouts.

6 Statistical Considerations

The SAS system version 9.4 (or higher), will be used for all analysis, unless otherwise specified.

6.1 TIMING FOR THE FINAL ANALYSIS

The final analysis will be performed according to a 2-stage process as detailed hereafter:

• Stage 1: end of the double-blind treatment period

The double-blind treatment period will be completed once the last subject last Week 24 visit will have been attended.

The date of the last subject last Week 24 visit will be referred to as the cut-off date for Stage 1. All the data collected until the cut-off date will be taken into consideration for a first database lock.

As a result, all the efficacy data required for the efficacy endpoints defined in Section 8.7 will be included in this first locked database.

This first database lock is requested by Genkyotex to enable Cmed to produce and deliver Top Line tables (see the list in Appendix 1) as soon as all Week 24 visit efficacy data has been collected, cleaned, and locked. This first database lock will also include all Week 28 follow-up visit data which will have been collected until the cut-off date and cleaned prior to the database lock. The second database lock (see Stage 2 below) is to be carried out once all remaining follow-up (V8) data has been collected and cleaned. Week 28 follow-up visit data not included in the first database lock will be listed separately in the clinical study report and in any other relevant document.

• Stage 2: end of the follow-up period

The follow-up period will be completed once the last subject last Week 28 follow-up visit will have been attended. It will be considered as the end of the study.

The date of the last subject last Week 28 follow-up visit will be referred to as the cut-off date for Stage 2.

All the data collected until the cut-off date will be taken into consideration for a second database lock. It will be regarded as the final database lock.

Cmed will produce and deliver both the remaining planned efficacy outputs and all the other planned outputs to Genkyotex after the final database lock.

6.2 MISSING DATA HANDLING

In the event of missing data at Week 24 visit for efficacy endpoints (see the list below), the Last Observation Carried Forward (LOCF) method will be applied by imputing Week 24 visit data with the last non-missing post-baseline data available at Week 12 visit (or at a later visit). If there is no non-missing post-baseline data or if the last non-missing post-baseline data is available at an earlier visit than Week 12 visit then the LOCF method will not be applied and no data will be imputed at Week 24 visit. Accordingly, the LOCF method will not be used for the interim analysis. The above-described use of the LOCF method for the imputation of missing data at Week 24 visit is based on recently published studies that have shown that the reductions in liver function tests are close to maximal effects after 12 weeks of treatment [2].

The LOCF method will be applied for the following efficacy endpoints:

- Primary efficacy endpoint;
- Week 24-defined secondary efficacy endpoints (except those defined for ELF and liver stiffness);
- Week 24-defined tertiary efficacy endpoint for total bile acids;
- Week 24-defined exploratory efficacy endpoints (except those from the assessments of the metabolomics signatures and additional biomarkers of interest)

The complete case approach will be applied for the analysis of categorical variables using a worst-case imputation strategy.

For all other analyses and summaries, no imputation will be performed other than to complete partial dates using standard imputation techniques as described below.

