#### The unblinded treatment code must not be recorded in the eCRF.

# 5.6.4 Reasons for Withdrawal

Subjects will be informed that they have the right to withdraw from the study at any time, without prejudice to their medical care, and that they are not obliged to state their reasons. Any withdrawal must be fully documented in the eCRF, and should be followed up by the Investigator.

The Investigator may withdraw a subject at any time if this is considered to be in the subject's best interest.

A subject MUST be withdrawn for the following reasons:

- Pregnancy or breast feeding.
- A change in UDCA dose during the treatment period.
- Confirmed or suspected DILI, as defined in Section 6.3.1.
- Confirmed or suspected liver decompensation, defined as hepatic encephalopathy, gastrointestinal tract bleeding due to esophageal varices, or ascites.

- Confirmed Grade ≥ 2 severity anemia without documented alternative cause, as defined in Section 6.3.2.
- Grade 3 severity AE recurring or not resolving after a pre-defined interruption and resumption of IMP (see Section 6.3).
- Any Grade 4 severity AE.
- Subject's withdrawal of consent.

The subject MAY be also discontinued for the following reasons:

- Protocol violations, including non-compliance and loss to follow-up. ٠
- Safety reasons.
- Administrative reasons.
- Other: the subject was withdrawn for a reason other than those listed above, such as termination of the study by the Sponsor (see Section 5.6.6).

A subject will be considered to have completed the study when he/she completes the final assessment visit of the follow-up period, i.e., Week 28 (Visit 8).

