# 5.6.5 Handling of Withdrawals

If the IMP is prematurely discontinued (i.e., before Week 24), the primary reason for discontinuation must be recorded in the appropriate section of the eCRF and all efforts must be made to complete and report the observations as thoroughly as possible. A premature end of treatment evaluation should be performed following the subject's withdrawal as described in Section 7.5, and recorded in the early termination eCRF page. A final follow-up visit should be performed within 4 weeks following the early termination visit, as described in Section 7.4.

If a subject fails to return for follow-up, attempts should be made to contact the subject to ensure the reason for not returning is not an AE. Likewise, if a subject decides to discontinue from the study, an attempt should be made to establish that the true reason is not an AE (bearing in mind subjects are not obliged to state their reasons). For subjects considered lost to follow-up, the eCRF must be completed up to the last visit performed.

Ongoing AEs should be followed up in accordance with the procedures described in Section 9.2.4.

Subjects who discontinue early will not be replaced.

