### 10.2 Sample Size Considerations

A sample size of 34 randomized and treated subjects within each treatment group with an overall sample size of 102 subjects will have 80% power to detect a 28% difference in the means of the percent change from baseline in serum GGT. A Wilcoxon Mann-Whitney test has been used for the sample size estimate because this represents the worst-case scenario with regards to statistical power. A standard deviation of 30 for the active GKT137831 group and a standard deviation of 40 for the placebo group have been assumed based on a recent phase 3 clinical trial of OCA [65].

An overall two-sided Type I error of 5% has been considered for the sample size estimate. The Hochberg method will be used to adjust the alpha level for multiple comparisons, therefore the first dose level comparison at the final analysis will be tested against an alpha level of 0.04695 and the second dose level will be tested against an alpha level of 0.023475. The alpha level of 0.023475 has been used for the sample size calculation.

The sample size calculation assumes all subjects, including withdrawals will be included in the analysis. Hence there has been no adjustment for dropouts.

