### 10.4.3.7 Missing Data/Outliers/Dropout Considerations

For the primary analysis all subjects will be included with missing data imputed using method MAR (missing at random) or MNAR (missing not at random), as appropriate. This same approach will be used regardless of whether an ANCOVA or Wilcoxon Mann-Whitney test is used to analyze the primary endpoint. More details, including sensitivity analyses, will be provided in the SAP. The complete case approach will be used for the analysis of categorical variables using a worst-case imputation strategy. For all other analyses and summaries no imputation will be performed.

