8.7 EFFICACY DATA ENDPOINTS AND ANALYSES

8.7.1 Primary Efficacy Endpoint and Analyses

The clinical response to GKT137831 is defined as the percent change from baseline to Week 24 visit in serum GGT (primary efficacy endpoint).

Absolute serum GGT values as well as absolute change and percent change from baseline to Week 24 visit in serum GGT values will be provided at baseline and Week 24 visit for each allocated treatment group using summary statistics.

Due to the small sample size, the primary analysis will be conducted using a stepwise approach. The percent change from baseline to Week 24 visit in serum GGT will be analyzed using an Analysis of Covariance (ANCOVA) with the allocated treatment and disease severity at baseline as fixed effects, and the serum GGT baseline value as a continuous covariate.

The least square means estimate of the difference between each dose of GKT137831 and placebo alongside the 95% confidence interval will be calculated. Given two doses of GKT137831 are tested versus placebo, the 97.5% confidence interval of the least square mean of the difference between each dose of GKT137831 and placebo will also be calculated to account for the multiple testing using Hochberg adjustment.

If the normality assumption for the primary analysis is not met then the percent change from baseline in serum GGT at Week 24 will be analyzed non-parametrically through a stratified Wilcoxon Mann-Whitney (van Elteren) test. The normality assumption will be assessed through the examination of diagnostic residual plots.

The primary analysis will be performed using the ITT population and a sensitivity analysis will be done using the PP population. If the Wilcoxon Mann-Whitney test is used, a subgroup analysis for disease severity will also be performed.

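### SAP 6.2 leaves early withdrawals out of the primary GGT analysis, although the protocol includes all subjects and the sample size assumes it; the change is not declared and no missing-data sensitivity analysis is designated

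*SAP*

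**What the plan says.** Protocol 10.4.3.7 sets the rule for the primary endpoint: "For the primary analysis all subjects will be included with missing data imputed using method MAR (missing at random) or MNAR", as appropriate, whichever of the two tests is used. It adds: "More details, including sensitivity analyses, will be provided in the SAP".

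The sample size rests on the same premise. Protocol 10.2 states: "The sample size calculation assumes all subjects, including withdrawals will be included in the analysis". SAP 5.4 repeats it: "The sample size calculation assumes all subjects (including withdrawals) will be included in the analysis". Both conclude that no dropout adjustment is needed. Protocol 5.6.5 adds: "Subjects who discontinue early will not be replaced".

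SAP 6.2 does something different. A missing Week 24 value is replaced by the last post-baseline value only if that value comes from Week 12 or later. If there is no post-baseline value, or the last one is "available at an earlier visit than Week 12 visit then the LOCF method will not be applied and no data will be imputed", Week 24 stays missing. SAP 6.4 opens the Week 12 window 64 days after first dose.

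On sensitivity analysis, SAP 8.7.1 says: "The primary analysis will be performed using the ITT population and a sensitivity analysis will be done using the PP population". SAP Section 7 produces PP outputs only if the PP set is at least 10% smaller than the ITT set. SAP Section 10 gives the 2-stage final analysis as the only change to planned analyses.

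**The concern.** The two documents disagree on who is in the primary comparison, and the SAP disagrees with the premise of its own power statement. A subject who stops early remains in the ITT set by definition (randomised and dosed at least once) but contributes no response to the test.

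Early loss need not be unrelated to treatment or to liver tests. The mandatory withdrawal reasons in protocol 5.6.4 include "Confirmed or suspected DILI, as defined in Section 6.3.1" and any Grade 4 adverse event. Leaving such subjects out can move the estimated difference. The protocol sent the sensitivity analyses that would examine this to the SAP, and the SAP designates none. If the question stays open until unblinding, the choice between the two rules could be made with results in view.

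**Working it through.** **1. Does SAP 6.2 remove subjects?** The ANCOVA and the van Elteren test each need a Week 24 percent change. With no observed value and no imputation there is no response, so the subject drops out. The deciding fact is whether any GGT exists from day 64 after first dose, not whether treatment stopped before Week 12, because SAP 6.4 assigns visits by date. Take the early termination visit to fall on the last dosing day and the follow-up visit g days later (protocol 5.6.5 allows up to 4 weeks). The subject is excluded when stop day + g ≤ 63:

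| Follow-up gap g | Stop days excluded |
|---|---|
| 28 | 1–35 |
| 14 | 1–49 |
| 7 | 1–56 |
| no follow-up visit | 1–63 |

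**2. Reproduce the stated power.** Inputs from SAP 5.4 and protocol 10.2: difference 28, SD 30 (active) and 40 (placebo), two-sided alpha 0.04695/2 = 0.023475, 34 per arm, Wilcoxon test.
- Root-mean-square SD = √((30² + 40²)/2) = 35.36.
- Noncentrality for a t-test = 28/(35.36 × √(2/34)) = 28/8.575 = 3.27, giving power 82.5%.
- With n multiplied by 3/π (Wilcoxon efficiency under normality), power is 80.5%. Direct simulation of the Wilcoxon test gives about 80%. The stated 80% reproduces, with all 34 per arm analysed.

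**3. Power if subjects are lost.** The documents give no dropout rate, so the losses are assumptions. The ANCOVA columns approximate the first-line analysis by a t-test with residual variance multiplied by (1 − R²), where R² is the share explained by the covariates, also assumed.

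| Lost per arm | Analysed per arm | Wilcoxon | ANCOVA, R² = 0 | ANCOVA, R² = 0.10 |
|---|---|---|---|---|
| 0 | 34 | about 80% | 82.5% | 86.6% |
| 2 | 32 | about 77% | 79.9% | 84.2% |
| 3 | 31 | about 76% | 78.4% | 82.9% |
| 5 | 29 | about 72% | 75.2% | 80.0% |

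Imputation does not restore lost information, so 80% is an upper bound for the Wilcoxon test under the protocol rule too. The table shows what the SAP's own statement is worth once its premise fails.

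**4. Size of a possible shift, for illustration.** Suppose k of 34 active subjects are excluded, would have had the placebo mean, and no placebo subject is excluded. A 28-point difference among those analysed is then 28 × (1 − k/34) in all subjects: 26.4, 25.5 or 23.9 for k = 2, 3 or 5, that is 1.6, 2.5 or 4.1 points less. The standard error of the difference is √(30²/34 + 40²/34) = 8.6, so this is about 0.2 to 0.5 standard errors. If the excluded subjects would have done better than those analysed, the sign reverses.

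**5. Does the PP analysis fill the gap?** It drops protocol deviators and does not vary the missing-data assumption. It may also not be produced: 0.9 × 102 = 91.8, so at least 11 of 102 subjects must be excluded from PP (at least 10 if 100 are randomised).

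**The case against.** The best reply is SAP 8.7.2. It specifies a repeated-measures ANCOVA of percent change in GGT in the ITT population, with treatment-by-visit interaction and unstructured covariance, reported at every post-baseline visit and listed among the Top Line tables. Such a model uses available visits under MAR, so a subject with only Week 2 or Week 6 GGT contributes. A reader might infer that no planned analysis would reveal the effect of the exclusions. The documents do not support that: the model's Week 24 estimate can be set beside the primary result, and disposition by arm with reasons (SAP 8.1) and missing counts (SAP 6.6) would show the loss. What remains is that the model is not designated for this purpose, cannot use subjects with no post-baseline GGT, gives way to visit-wise analysis if it does not converge or normality fails, and gives no MNAR result. SAP 6.2 also applies LOCF to secondary endpoints defined at Week 24, so it is unclear whether the model's Week 24 input is observed or carried forward.

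Second, the protocol left details to the SAP, and SAP 6.2 states its LOCF rule openly with a rationale (near-maximal effect after 12 weeks). That stands as a defence of carrying Week 12 values forward. It does not defend leaving earlier withdrawals out, since the protocol delegated the method and not whether subjects are included.

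Third, the wording in SAP 5.4 is a sizing assumption, not an inclusion rule. That is correct; the rule itself is in protocol 10.4.3.7.

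A reader might also infer from SAP 6.4 that off-drug values must be barred. Date-based windowing does let a follow-up GGT become a carried-forward value: stopping on day 50 with follow-up on day 78 gives a Week 12 value, and stopping on day 90 with follow-up on day 118 gives a Week 18 value that displaces the on-drug Week 12 value. But SAP 6.4 covers any assessment in the window, and using post-discontinuation values in an ITT analysis is a legitimate choice. Barring them while keeping LOCF would exclude more subjects.

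**Conclusion.** The conflict is in the text and needs no assumption: protocol 10.4.3.7 includes all subjects, SAP 6.2 does not, SAP 5.4 assumes that they are included, and SAP Section 10 is silent. It is also plain that no missing-data sensitivity analysis of the primary endpoint, and no MNAR analysis, is designated.

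The size is conditional. For assumed losses of 2 to 5 per arm, the Wilcoxon power cost is about 3 to 8 percentage points, and ANCOVA with modest covariate gain could absorb it. The illustrative shift is under half a standard error and depends on one-sided loss at the placebo mean. A reader might infer that the trial is underpowered or its estimate biased in a known direction; without a dropout rate, the documents support neither. This is a should-fix point.

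**What to change.** In SAP 6.2 and 8.7.1:
- Include every ITT subject in the primary analysis by a method consistent with protocol 10.4.3.7, for example multiple imputation under MAR from visit-wise GGT, with a stated rule for pooling if the van Elteren fallback is used.
- Add one MNAR sensitivity analysis (placebo-based or delta), produced whatever the size of the PP set.
- Keep LOCF as a sensitivity analysis.
- State that the Week 24 estimate of the repeated-measures model, on observed data without LOCF, is reported as supportive.
- Say whether carrying an off-drug follow-up GGT forward as Week 12 or Week 18 is intended.

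The cost is SAP wording and modest programming before unblinding. No protocol amendment is needed, because the protocol already specifies this approach.

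If LOCF with exclusions is kept instead, declare it in SAP Section 10, correct the statements that all subjects are analysed in SAP 5.4 and in protocol 10.2 and 10.4.3.7, and restate power for the expected early loss. That route means changing the protocol text as well, and a less favourable power figure. Editing the SAP alone would leave the two documents in conflict.
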